## **Ultrasound-guided Pectoralis 1 and 2 block with liposomal bupivacaine for breast surgery: A prospective randomized study.**

**Design:** Level I randomized prospective outcomes study comparing two groups of patients. One group will receive liposomal bupivacaine for a pectoralis (“Pec”) block infiltration and the other will receive incisional bupivacaine infiltration by the surgeon.

**Sample Size:** 112 patients

**Study Duration:** Approximately 18 months

**Population:** Patients presenting to the University of Minnesota Medical Center, M health Ambulatory Surgery or Fairview Maple Grove Clinics Ambulatory Surgery Center, for elective lumpectomy and partial mastectomy procedures +/- axillary node dissection.

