### **Secondary Objectives:**

1. To determine if a pectoralis 1 and 2 block with liposomal bupivacaine provides decreased maximal pain scores when compared to incisional bupivacaine infiltration
2. To determine if a pectoralis 1 and 2 block with liposomal bupivacaine provides decreased rate of conversion to general anesthetic when compared to incisional bupivacaine infiltration
3. To determine if a pectoralis 1 and 2 block with liposomal bupivacaine improves quality of recovery score post-operatively when compared to incisional bupivacaine infiltration.
4. To observe the effect on chronic postoperative pain in patients who have breast surgery.

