**Exclusion criteria:**

- Patient on chronic anticoagulation
- Pregnant women
- Non-english speaking patients
- Any individuals who are unable to give informed consent
- Any individual with diminished capacity to give informed consent
- Allergy to local anesthetics
- Patients who remain intubated overnight after surgery or who are unable to provide information regarding their pain immediately postoperatively
- Daily use of opioid for more than three weeks
- Significant liver disease, defined as liver enzymes greater than 3x the upper limit of normal
- Lack of patient cooperation including those patients who refuse a MAC anesthetic
- Patient with pectoral muscle involvement of tumor
- Contraindication to regional anesthesia
  - Infection at injection site
  - Inability to guarantee sterile equipment or sterile conditions for the block
  - Patient refusal
  - Severe Coagulopathy or bleeding disorder

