**Randomization procedure:**

Patients will be identified by members of the treatment team in either the surgeon's clinic, pre-assessment clinic, or preoperative area. Patients who have opted out of research will not be asked to participate in the study. Patients will be approached to consent for the study by a surgeon, anesthesiologist, or member of the research team. Patients who agree to participate in the study will sign both a study consent and HIPAA authorization allowing the use of specified information contained in medical records for research purposes.

A random number generator will be used to determine if the patient will have pectoralis liposomal bupivacaine infiltration or bupivacaine infiltration directly into the incision space. The primary or co-investigator will access the number generator in the pre-op area. The website [www.random.org](http://www.random.org) will be used as the random number generator.

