For the surgeon infiltration, the patient will be brought directly to the operating room where intraoperative anesthetic with an opioid-sparing MAC technique will be provided as described below. Just prior to the skin incision, 0.25% bupivacaine will be used to infiltrate the dermis and subcutaneous space in the proposed incision. Throughout the procedure, additional incisional bupivacaine infiltration into the surrounding tissues will be performed as needed for local anesthesia. A total of up to 30 mL of 0.25% bupivacaine will be divided equally for the two sides of the incision. An additional 5 mL of 0.25% bupivacaine will be infiltrated into the pectoralis major muscle at the deep margin of resection. Accidental intravascular injection is minimized by continuous needle movement and frequent aspiration.

The following vital signs will be monitored throughout the procedure: Heart rate, blood pressure, oxygen saturation, and respirations, and patient's state of consciousness. We will monitor the patient until they are brought to the operating room for surgery.

All patients will receive multimodal analgesia in the preoperative area. They will receive 975 mg of oral acetaminophen and 300 mg of gabapentin orally prior to surgery. The intraoperative anesthetic will be an opioid-sparing MAC anesthetic. If patients are unable to tolerate procedure under MAC they would be converted to a general anesthetic with an laryngeal mask airway (LMA). For those patients receiving a lumpectomy with axillary dissection, they will receive a general anesthetic with LMA. Patients will receive IV midazolam 0-2 mg followed by 40-100mg of IV lidocaine, and followed by a propofol infusion and a 0.25 mg/kg bolus of ketamine followed by 0.25 mg/kg /hour infusion of ketamine. Opioids will be avoided unless HR or BP increases by 20 % above baseline. Then only short acting opioids (fentanyl) will be given.

In the recovery room if the patient experiences pain greater than 5/10 they will receive either IV or oral pain medications. If pain score is less than 5 patients will get non opioid medications unless the patient desires an opioid medication.

When the operation is complete the patient will either be brought to the PACU or Phase II. Each day a member of the research team will contact and evaluate the patient for signs of complications and ask the patient their minimum and maximum pain score

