### **Outcome Measurements:**

Outcome measures include both clinical assessments and subjective outcome measures reported by the subject on different rating scales.

Distribution of the scores and the clinical evaluations will be examined and cut-points may be assigned to create categorical data. Statistical analysis of parametric data will be done using ANOVA techniques with corrections for repeated measures (when necessary); non-parametric data will be analyzed with Chi-squared techniques. Statistical significance will be defined as  $p < 0.05$ . Power is expected to be 0.8. Data stratification will be done where appropriate. Stratification variables include: pre-operative pain modality.

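### The only named stratification variable cannot be applied as written, while axillary dissection, which brings a general anaesthetic by protocol, is named in no analysis

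*Combined protocol and SAP*

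**What the plan says.** Under Outcome Measurements, the plan proposes ANOVA for parametric data and chi-squared techniques otherwise, with stratification where that is judged appropriate. The only variable named is given in one sentence: "Stratification variables include: pre-operative pain modality". No levels are listed and the term appears nowhere else.

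The design summary defines the population as patients presenting "for elective lumpectomy and partial mastectomy procedures +/- axillary node dissection". Treatment technique then separates two anaesthetic pathways. Most patients start under monitored anaesthesia care (MAC), but "For those patients receiving a lumpectomy with axillary dissection, they will receive a general anesthetic with LMA".

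The Randomization procedure states only that "A random number generator will be used to determine if the patient will have pectoralis liposomal bupivacaine infiltration" or the comparator, with no strata. Data collection lists the type of surgery. Neither Statistical Considerations nor Outcome Measurements names axillary dissection, type of surgery or type of anaesthetic as a stratum, covariate or subgroup.

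**The concern.** An analyst told to stratify by pre-operative pain modality has to guess what it is, and each main reading the documents offer is unusable or weak.

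Meanwhile, a factor with a clear clinical definition, which changes the anaesthetic by protocol and plausibly changes opioid use, is left out of the analysis. With no stratification at randomisation, the dissection share can differ between arms by chance. An unadjusted analysis also leaves any dissection-related spread in the residual variance. Outcome Measurements already allows cut-points to be set after distributions are examined. A covariate picked at that stage would be a second choice open to the data, which naming the factor beforehand would avoid.

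**Working it through.** **Readings of the named variable**

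- *Premedication.* Treatment technique says "All patients will receive multimodal analgesia in the preoperative area", with the same two oral drugs for everyone. The variable then has one level.
- *Analgesic technique.* Treatment technique and Assessments use 'modality' and 'mode of analgesia' for the technique received, and the technique is what is randomised. The variable is then the arm, and no treatment contrast is left within a stratum.
- *Prior opioid use.* Exclusion criteria remove "Daily use of opioid for more than three weeks", so only lighter or shorter use remains.

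**The plan's own sample size**

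Statistical Considerations gives 56 per group, 80% power, a 35% decrease and alpha 0.05. It gives no SD, control mean or sidedness, so the figure can only be solved backwards. For a two-sided t-test with 56 per group and 80% power, the standardised effect is d = 0.534. The implied coefficient of variation is CV = 0.35/0.534 = 0.655. This is circular by construction. It anchors the illustration and does not check the sample size.

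**Illustrative gain from adjustment**

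Assumed, not in the documents: dissection share s; opioid use k times higher with dissection; the 35% decrease proportional in both strata; normal errors; 0.655 as the total CV.

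- Gap between strata in the control arm, as a fraction of the control mean: (k − 1)/(1 − s + s·k). In the treated arm it is 0.65 of that, so the average factor is (1 + 0.65)/2 = 0.825.
- Variance explained: R² = s(1 − s)·[0.825·gap/0.655]².
- Adjusted power: t-test power at d/√(1 − R²) with 109 degrees of freedom.

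Worked case, s = 0.2 and k = 2: gap = 1/1.2 = 0.833; R² = 0.16 × (0.825 × 0.833/0.655)² = 0.176; power 87.0%. This is equivalent to 56/(1 − 0.176) = 68 per group.

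| Share | Ratio 1.25 | Ratio 1.5 | Ratio 2 |
|---|---|---|---|
| 5% | 80.2% | 80.7% | 82.7% |
| 10% | 80.3% | 81.3% | 84.7% |
| 20% | 80.6% | 82.1% | 87.0% |
| 30% | 80.7% | 82.5% | 87.8% |

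Simulation (40,000 trials per cell, additive factor fitted) gave 81.5% and 86.3% at a 20% share and 82.1% and 87.4% at a 30% share, for ratios 1.5 and 2. Unadjusted power was 79.9-80.2%. With no prognostic effect (ratio 1), adjusted power was 79.4-79.8%, so the cost of adjusting needlessly is under one point.

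**Chance imbalance**

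By exact binomial calculation with 56 per arm, the arms differ in dissection share by 10 points or more in about 2% of trials at a true share of 5%, 19% at 20% and 26% at 30%. Each 10 points shifts the unadjusted estimate by 10 × 0.825 × gap. At shares of 20-30% and ratios of 1.5-2 that is 3.6-6.9% of the control mean, against a 35% target. Adjustment removes this shift. The benefit is already inside the power figures and is not additional to them.

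**The case against.** The strongest objection is that only the undefined term is a defect, and that adjusting for dissection is a preference. Much of this stands. Randomisation keeps the unadjusted comparison unbiased. The wording about stratification is open-ended, so adjustment for surgery type is not ruled out; it is merely not pre-specified. A reader might infer that the primary result would be confounded by dissection or that the plan forbids adjustment. The documents support neither.

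The size is also uncertain. Nothing in the documents supports a 20-30% share in particular. Inclusion is worded as partial mastectomy, and MAC is the default, so a low share is equally possible.

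A further reading of the stratifier is the amount of opioid given pre-operatively, which Data collection lists and which could vary between patients. The documents do not connect the two or say that this amount is fixed before randomisation, so the variable stays undefined. The document's own usage does lean towards the technique reading, which is the one that duplicates the arm.

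A reader might also infer that planned general anaesthetics would count as conversions in the secondary objective that the block "provides decreased rate of conversion to general anesthetic when compared to incisional bupivacaine infiltration". Treatment technique answers that: "If patients are unable to tolerate procedure under MAC they would be converted to a general anesthetic". A protocol general anaesthetic is therefore not a conversion. Only the denominator is unstated, which is a minor clarification and not part of this point.

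**Conclusion.** The point holds as a low-cost improvement. The named stratifier cannot be applied as written, and that rests on the text alone. The case for axillary dissection rests on the protocol tying it to a different anaesthetic and on a plausible, unproven effect on opioid use.

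Under the assumptions listed, power moves from 80% to about 80-83% at a 5% share and about 81-88% at a 20-30% share, for opioid ratios of 1.25 to 2. These figures are illustrative, and nothing in the documents places this trial within the range. If dissection is rare or weakly prognostic, the gain is close to nil, and correcting the undefined variable is then the main benefit.

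**What to change.** Under Outcome Measurements, replace the stratification sentence with: 'The analyses of total opioid use and of pain scores will include planned axillary dissection (yes/no), as recorded before randomisation and whatever operation is then done, as a factor in the ANOVA.' Using the plan rather than the operation performed keeps the factor free of anything that happens after allocation.

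Delete pre-operative pain modality unless it is defined, with levels, as a factor that varies between patients before randomisation. In that case keep it as a second factor.

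The cost is SAP wording, one degree of freedom and one yes/no field completed before randomisation. The field is needed because the surgery type listed under Data collection may record only the operation done. No change to treatment, anaesthetic or sample size is required.

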### **Stopping Criteria:**

This study will be stopped if 5% of the subjects experience local toxicity. If  $\geq 10\%$  of the subjects develop an infection at the injection site, the protocol will be discontinued. Additionally, if any patient experiences a serious adverse event as a result of the study medications as determined by the principle investigator, they will be discontinued from the study.

Local anesthetic toxicity is defined as patients who experience local anesthetic toxicity symptoms such as new onset of tinnitus, metallic taste in mouth, numbness around lips, seizures, heart block or new arrhythmia after injection of local anesthetic for up to monitoring period of 5 days.

**Notification:** When a study participant, voluntarily or involuntarily, is eliminated from the study protocol, the Principal Investigator and Associate Investigators will be notified.

**Adverse reactions:** Adverse or unexpected occurrences resulting from the treatment utilized in the protocol will be reported to the Principal Investigator and the Associate Investigators. These individuals will discuss these reactions or untoward events and implement changes in the protocol accordingly. Investigators will meet regularly to discuss problems encountered with the study protocol.

**Modifications to protocol:** Alterations that may become necessary in the protocol during the study period will be made by agreement of the investigators. Patients will be notified of any relevant protocol changes.

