**Risks:**

Risks to subjects of this study include

- Failure of the block
- Wound infections
- Complications related to placement of the Pec block including
  - lung perforation, nerve injury or intravascular injection.
- Local anesthetic toxicity

These complications all fall within the standard risks of surgery. Any intervention being provided as a part of this study falls within the standard of care of Pec infiltration and surgeon infiltration and are within the standard treatments for post-operative pain and are currently used as analgesic options at UMMC. There may also be certain unforeseen risks that will be treated as necessary by the operating physician. All complications will be noted by the operating physician and reported to the IRB and research staff. Appropriate records will be made in the patient chart, and the patient will be treated as needed by the operating physician.

Any unforeseen injuries that may occur to the subjects while enrolled in this study will be treated as needed by the operating physician. No provision has been made for financial payments or other forms of compensation (such as lost wages, medical cost reimbursement, lost time or discomfort) with respect to such injuries. No arrangement has been made for further compensation from UMMC. However, patients do not waive any legal rights by signing a consent form.

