  - Amount of opioids left over after 3 days
  - Presence of nausea/vomiting in 3 days post operatively
  - Occurrence of any subsequent re-admission over the ensuing 1 month and any complications

The collected data will be compared between groups on a regular basis in order to evaluate the safety and efficacy of the study. All data will be stored in secure locations in the Research Office. Research coordinators working with physicians to collect data at appropriate intervals will ensure complete follow-up. Research coordinators will periodically check physician schedules to ensure that patients being seen for follow-up complete all required questionnaires. Monthly meetings will also be conducted to ensure all patients needing to be evaluated are seen at the appropriate time intervals and that all data is being entered into the appropriate database.

**Data Safety Monitoring:** Authorized study staff and investigators who have gone through HIPAA, CITI, and other data security training through the University of Minnesota will be collecting, managing, and analyzing data. All serious adverse events will be brought forward to the Anesthesia Data Safety Monitoring Board that is comprised of various senior staff anesthesiologists. A formal determination concerning the severity of the risk and the recommended actions required will be submitted in writing to the principle investigator. This report will be submitted to the Institutional Review Board along with the required UPIRTSO documents.

**Statistical Considerations:** The primary outcome measurement used in this study is total opioid use

A sample size of 112 (56 per group) will be enrolled in order to power our study at 80% to detect a 35% decrease in total post-operative opioid usage for our treatment group versus the control with an  $\alpha=0.05$ . This sample size was estimated based on previous estimates for postoperative analgesic consumption from similar trials reported in the Tam (2015) meta-analysis paper.

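### The 5% toxicity and 10% infection stopping limits name no denominator, minimum number treated or arm, and neither plain reading of them works well

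*Combined protocol and SAP*

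**What the plan says.** The Stopping Criteria section of the combined protocol and SAP has two numeric triggers. For toxicity: "This study will be stopped if 5% of the subjects experience local toxicity". For infection, at 10% or more, "of the subjects develop an infection at the injection site, the protocol will be discontinued". The same section defines toxicity to include mild symptoms (tinnitus, metallic taste, perioral numbness) as well as seizures and cardiac rhythm events, over up to 5 days. A patient with a serious drug-related event, "as determined by the principle investigator, they will be discontinued from the study".

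Statistical Considerations fixes the size: "A sample size of 112 (56 per group) will be enrolled". No section says whether the percentages refer to patients treated so far, enrolled or planned. None gives a minimum number, an arm or a checking schedule for them.

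Other safety routes exist. Under Risks: "All complications will be noted by the operating physician and reported to the IRB and research staff". Under Data collection: "The collected data will be compared between groups on a regular basis in order to evaluate the safety and efficacy of the study". Under Data Safety Monitoring: "All serious adverse events will be brought forward to the Anesthesia Data Safety Monitoring Board". Under Adverse reactions, the investigators confer: "These individuals will discuss these reactions or untoward events and implement changes in the protocol accordingly". None of these carries a number.

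**The concern.** These are the plan's only numeric safety triggers. Two people applying them in good faith to the same data could reach opposite decisions: one stops at the first metallic taste, the other waits for a sixth case.

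Exposure also differs by arm. Under Treatment technique, the Pec arm receives 20 mL liposomal bupivacaine (5 + 15) and 20 mL of 0.25% bupivacaine (10 + 10), with up to 40 mL more from the surgeon. Controls receive up to 30 + 5 = 35 mL of 0.25% bupivacaine, no liposomal drug and no block. A limit counted over both arms dilutes harm confined to one of them.

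It is also unsaid whether a patient who is discontinued or eliminated still counts. Enrollment procedures has the study records of eliminated patients shredded and leaves those patients out of the final analysis.

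**Working it through.** The plan states no operating characteristics for these limits, so there is no figure to reproduce. Inputs from the plan are 112 patients, 56 per arm, and limits of 5% and 10%, each read as reached or exceeded. The event rates are my assumptions, shown as a range, because the documents give none.

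**Counts implied by each reading**
- Running rate: 1/n ≥ 0.05 when n ≤ 20, and 1/n ≥ 0.10 when n ≤ 10. One event that early stops the trial.
- Share of 112: 0.05 × 112 = 5.6, so 6 toxicities; 0.10 × 112 = 11.2, so 12 infections. If all fall in the Pec arm, 6/56 = 10.7% and 12/56 = 21.4%.
- By arm: 0.05 × 56 = 2.8, so 3 toxicities; 0.10 × 56 = 5.6, so 6 infections.

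**Methods.** Running rate: exact recursion over patients 1 to 112, arms alternating, stopping when events/treated reaches the limit after any patient. Share of 112: P(X ≥ 6) or P(X ≥ 12), with X the sum of two binomials of size 56. By arm: 1 − P(Pec count < r) × P(control count < r), with r = 3 or 6.

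| True rate, Pec / control | Running rate | Share of 112 | By arm |
|---|---|---|---|
| Toxicity 1% / 1% | 20% | 0.1% | 4% |
| Toxicity 2% / 2% | 40% | 2.5% | 19% |
| Toxicity 3% / 3% | 58% | 12% | 42% |
| Toxicity 10% / 0 | 84% | 49% | 93% |
| Toxicity 10% / 2% | 91% | 67% | 94% |
| Infection 2% / 2% | 20% | <0.1% | 0.2% |
| Infection 5% / 5% | 50% | 1% | 12% |
| Infection 20% / 0 | 89% | 45% | 98% |
| Infection 20% / 2% | 93% | 59% | 98% |

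**Where the running-rate false stops arise.** At 2% toxicity, P(at least one event in the first 20) = 1 − 0.98^20 = 0.332. So 33 of the 40 percentage points come from a single event in the first 20 patients. Checking every 6 patients barely helps (37%).

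**Share of 112 above its limit.** Pec 15% / control 0 stops in 86%, Pec 20% / control 0 in 98%, and 10% in both arms in 97%.

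**Timing, Pec toxicity 10% / control 0.** After 20 patients (10 Pec), the running rate has fired with probability 1 − 0.9^10 = 65%, and the by-arm count with P(X ≥ 3 of 10) = 7%. After 56 patients (28 Pec), the figures are 77% and 54%.

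**Pooled running rate with a minimum.** Starting checks at patient 40 gives false toxicity stops of 7%, 23% and 43% at 1%, 2% and 3%; Pec 10% with control 0 to 2% is detected in 77% to 87%. Requiring two events gives the same totals for toxicity: two events reach 5% only up to patient 40 (2/40), and such a pair is still present when checks begin there. For infection the two minimums differ. Two infections reach 10% only up to patient 20 (2/20), so a two-event minimum equals starting at patient 20, with false stops of 6.7% and 34% at 2% and 5%. A 40-patient minimum needs four infections at patient 40 (4/40).

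**Arm size.** Randomization procedure describes a random number generator without blocking. Under simple allocation the 95% range for one arm is 46 to 66 (56 ± 1.96 × √(112 × 0.25) = 56 ± 10.4). By-arm detection of Pec toxicity 10% / control 0 then runs from 85% to 97%.

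**The case against.** The best defence is that one clarifying sentence would cure the gap, and that a limit by arm is a design preference. Much of this stands. Pec toxicity of 10% with control 0 is 5% overall, and Pec infection of 20% with control 0 is 10% overall. Both sit exactly at a pooled limit, where any fixed share fires about half the time. A reader might infer from 49% and 45% that the share-of-112 reading misses real harm; its performance at higher Pec toxicity rates does not support that.

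A reader might also infer that the plan deliberately pools the arms. Pooling is the plain sense of the wording, but it is not stated, and Data collection does provide for safety comparison between groups.

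Nor do the documents show that toxicities in eliminated patients disappear. Assessments has complications recorded from consent to last follow-up, and Risks and Precautions and corrective actions require chart entries and reports to the IRB. What remains is narrower: the plan does not say that such patients count towards the limits.

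Finally, the running-rate figures assume a check after every patient from the first, which the plan does not prescribe. A minimum number lowers them, but the plan gives none. The other safety routes do not fill the gap either: the board receives serious events, while tinnitus, metallic taste and lip numbness will often not be serious.

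**Conclusion.** The concern holds as a gap in the definition of the stopping limits. Depending on the reading, toxicity of 2% in both arms stops the trial in 40% or 2.5% of cases, and Pec toxicity of 10% with control 0 stops it in 84% or 49%. The running reading lets one mild early symptom end the trial. The share-of-112 reading waits for an observed Pec toxicity of 10.7% if all events are in that arm, although it performs well once Pec toxicity reaches 15% to 20%.

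The missing denominator, minimum and arm are plain from the text and do not depend on any rate. How much they matter does depend on the assumed rates. The documents do not support a claim that the trial lacks safety oversight, and the efficacy analysis is untouched.

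**What to change.** State that the limits apply to every treated patient, including those later discontinued or eliminated, whatever Enrollment procedures says about their records, and that they are monitored by arm. The third local anesthetic toxicity or the sixth injection-site infection in either arm (5% and 10% of the planned 56, rounded up) pauses enrolment, and the existing Anesthesia Data Safety Monitoring Board decides whether to stop. Because a fixed count is slow early, each seizure, new arrhythmia or heart block goes to the board at once.

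The change costs protocol wording and a short table of operating characteristics, with no added patients. The plan should state the downsides: false toxicity pauses of 4%, 19% and 42% at 1%, 2% and 3% in both arms, slower early firing than a running rate, arm sizes that may differ from 56, and a board that sees counts by arm. Each trigger is a pause and not an automatic stop.

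If the sponsor keeps a pooled rule, it should be defined as a rate among treated patients with a stated checking schedule and a minimum of two events or 40 treated. For toxicity the two minimums have the same overall stopping chance, but the two-event form can act before patient 40. For infection they differ, so the plan must name one.
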